Smartphone-based CBT for OCD can address gaps in access to treatment, offering standardized, high-quality, empirically-based interventions in a low-cost and accessible format. Additionally, given the low rate of doctoral-level clinicians specializing in CBT for OCD treatment, it would be advantageous to establish whether mobile app-based CBT can be administered effectively with assistance from trained bachelors-level coaches who are supervised weekly by licensed, doctoral-level psychologists. This would greatly enhance scalability of the treatment.

II. SPECIFIC AIMS

The overarching purpose of this project is to test the feasibility, acceptability, and efficacy of mobile-app-delivered CBT for OCD. We accomplish this through Specific and Exploratory Aims 1-3.

Specific Aim 1: In a well-powered, randomized-controlled trial, we will test the efficacy of the active treatment arm (Perspectives OCD) compared to a supportive attentional control (HealthWatch) in reducing primary (i.e., OCD symptom severity, measured via Y-BOCS) and secondary outcomes (e.g., quality of life, depression, social and occupational functioning) at week 12.

Primary Hypothesis: We hypothesize that participants receiving app-based CBT for OCD will have greater improvement in Y-BOCS scores than those in the supportive attentional control condition at treatment endpoint (week 12).

Secondary Hypothesis: We hypothesize that participants receiving app-based CBT for OCD will have greater improvement on secondary clinical outcome measures (i.e., depression (QIDS-SR), functional impairment (WSAS), and quality of life (Q-LES-Q)) than those in the supportive attentional control condition at treatment endpoint (week 12).

Exploratory Aim 2: Feasibility and Acceptability

Hypothesis: We hypothesize that app-delivered CBT for OCD will be feasible (based on drop-out rates) and acceptable (based on descriptive statistics of patient satisfaction, app use, and app feedback as well as qualitative feedback) to individuals with OCD.

Exploratory Aim 3: Maintenance of gains (Y-BOCS, QIDS-SR, Q-LES-Q-SF, WSAS) at follow-up (week 24).

Hypothesis: There will be no significant difference between the primary and secondary outcomes measured at treatment endpoint (week 12) and end of follow-up (week 24) in the group that participated in the app-CBT condition.

III. SUBJECT SELECTION

Overview:

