Upon initiating the app-based CBT treatment, each participant will be assigned a BA-level coach with prior training in CBT and some familiarity with OCD; coaches will be supervised weekly by a licensed psychologist (see "Coach Training and Qualifications," below) and all coach calls will be recorded for fidelity (see "Ongoing Monitoring of Coaching Fidelity" below). The coach will have a brief onboarding phone call to introduce themselves and orient participants to the treatment. Participants can communicate asynchronously with their coach through a secure messaging system incorporated into the app throughout the 12-week treatment. The coach will have a separate administrative interface to the study service which is accessible from inside the Partners firewall and allows the coach to respond to these in-app communications from patients. The coach communication aims to provide support and additional motivational enhancement to patients, and to provide feedback about the skills and homework that the patient is learning through the app. Patients will be notified that the coach will respond to all in-app communications within 36 hours on weekdays. Moreover, brief phone check-ins may be arranged between the participants and coaches on an as-needed basis to supplement the chat system (e.g., to more thoroughly answer a participant question about a skill, help set goals for 2nd half of treatment at treatment mid-point, evaluate and enhance motivation). Participants have access to the Perspectives app and coach support throughout the 12-week treatment. During the initial 3-month follow-up phase of the study, participants will continue to have access to the Perspectives app, but without the coach support or messaging system.

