Baseline differences between the treatment arms in demographic and other potential prognostic variables will be examined using chi-square analyses for discrete variables (if prevalence >10 in the treatment arm with the lower prevalence, or Fisher’s exact test if not) and t-tests for continuous variables. Prior to data analysis, all major variables will be screened for inconsistent or abnormal values. Continuous measures will be assessed for skewness and outliers (based on model residuals), and, if needed, will be transformed to better meet modeling assumptions of normality and homogeneity of variance. A two-tailed p-value $<.05$ will be considered evidence of statistical significance for the primary and secondary outcomes. Our primary and secondary analyses will use generalized linear mixed-effects models (GLMMs). GLMMs can easily accommodate nesting of repeated observations within subjects, include all who complete at least one assessment (including the baseline assessment), and are the preferred method to analyze longitudinal data (Hamer and Simpson, 2009). Despite our best efforts to retain participants, we do expect dropouts (subjects who are lost to follow-up or withdraw early from the study). We will attempt to perform all scheduled assessments for subjects who are withdrawn from the protocol and will provide financial incentives for participation in assessments. Our intent-to-treat sample will include all randomized patients who complete at least one assessment, making our

primary and secondary analyses intent-to-treat analyses. We will also perform “per protocol” analyses. Our per protocol population will include all randomized patients who complete the baseline and post-treatment assessments, and who did not initiate prohibited treatment during the study. We will repeat our GLMM analyses using the per protocol sample. Dropout, study withdrawal, and loss to follow-up will be tabulated by reason and treatment arm. Analyses will be conducted to ascertain to what extent dropouts are nonrandom, and, if so, what factors are associated with dropout. To evaluate potential attrition bias, study dropouts will be compared to study completers.

A. Specific data variables being collected for the study (e.g., data collection sheets)

Specific variables being collected and their timeline are presented above, in Tables 1 and 2, and described in the Study Procedures section.

B. Study endpoints

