Primary endpoint: Difference in OCD severity (Y-BOCS) at the end of treatment (i.e., week 12 assessment).

Hypothesis 1: Participants receiving app-CBT will have lower Y-BOCS scores than those in the supportive attentional control condition at treatment endpoint (week 12).

Secondary endpoints: Difference in secondary clinical outcomes at the end of treatment (i.e., week 12 assessment)

Hypothesis 2: Participants who receive the app-CBT will have better scores on secondary clinical outcome measures than those in the supportive attentional control condition at treatment endpoint (week 12) with respect to:

H2.1: depression severity, as measured by the QIDS-SR, where lower scores are better.

H2.2: functional impairment, as measured by the WSAS, where lower scores are better.

H2.3: quality of life, as measured by the Q-LES-Q-SF, where higher scores are better.

Exploratory endpoint 1: Feasibility and Acceptability

Hypothesis 3.1: Drop-out from app-delivered CBT for OCD will not be higher than drop-out from the supportive attentional control condition, which will indicate feasibility.

Hypothesis 3.2: Patient satisfaction ratings (i.e., CSQ total scores) in the group receiving app-delivered CBT for OCD will not be lower than those in the supportive attentional control condition, which will indicate acceptability.

Hypothesis 3.3: App-delivered CBT for OCD will be acceptable to individuals with OCD based on descriptive statistics of app use, app feedback, and qualitative feedback comments.

Exploratory endpoint 2: Maintenance of gains (Y-BOCS, QIDS-SR, WSAS, Q-LES-Q-SF) during follow-up (at 3-month and 12-month follow-up assessments).

Hypothesis 4: At the 12-month follow-up assessment, participants who received app-CBT will have lower Y-BOCS scores than those in the supportive attentional control condition.

Exploratory endpoint 3: Treatment utilization for OCD concerns following the 3-month follow-up.

Hypothesis 5: Participants assigned to the app-CBT treatment condition will be less likely to seek additional treatment for OCD than participants assigned to the supportive attentional control condition prior to the 12-month follow-up assessment.

C. Statistical methods

For all statistical analyses, we will use a Type I error probability of 0.05 to determine significance unless otherwise noted.

Primary endpoint: Difference in OCD severity (Y-BOCS) at the end of treatment (i.e., preliminary efficacy for primary OCD symptoms)

Analysis:

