- H3.2: We will analyze patient satisfaction, as measured by on Client Satisfaction Questionnaire (CSQ) in a hierarchical mixed model (i.e., GLMM) that will include time (categorical; week 6 and week 12), treatment (app-CBT vs. supportive attentional control), and their interaction as fixed effects, and will model time as a repeated measure using a compound symmetry covariance structure. We will test group differences with one-tailed tests in patient satisfaction (testing for lower satisfaction) at both week 6 and week 12 using specific contrasts with $\alpha=.025$ to adjust for multiple testing. Non-significant results of these tests will be interpreted as indications of treatment acceptability, while lower satisfaction will be interpreted as indicating a lack of acceptability.
- H3.3: Quantitative (i.e., app feedback questionnaires, uMARS) and qualitative participant feedback about app features will be summarized for the app-CBT group using descriptive statistics.

Exploratory endpoint 2: Maintenance of gains (Y-BOCS, QIDS-SR, WSAS, Q-LES-Q-SF) at follow-up (week 24).

Analysis:

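### Exploratory Aim 3 frames week-24 maintenance as no significant change from week 12, with no direction or margin, so further improvement contradicts it and an imprecise partial loss agrees with it

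*Combined protocol and SAP*

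**What the plan says.** Section II introduces the aim as "Exploratory Aim 3: Maintenance of gains (Y-BOCS, QIDS-SR, Q-LES-Q-SF, WSAS) at follow-up (week 24"). Its hypothesis is "There will be no significant difference between the primary and secondary outcomes measured at treatment endpoint (week 12) and end of follow-up (week 24"), and the comparison is made "in the group that participated in the app-CBT condition". So it is a within-arm comparison of two visits for four outcomes, with no stated direction, margin or confidence-interval rule.

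On significance, section VI.C says "we will use a Type I error probability of 0.05 to determine significance unless otherwise noted". The opening of section VI says "A two-tailed p-value $<.05$ will be considered evidence of statistical significance for the primary and secondary outcomes". No one-tailed exception is given for Aim 3.

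Under Treatment Format in the study procedures, for the initial 3-month follow-up, "participants will continue to have access to the Perspectives app, but without the coach support or messaging system".

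Section VI treats the same endpoint differently. Section VI.B lists maintenance at 3 and 12 months, but its Hypothesis 4 is a between-arm Y-BOCS difference at 12 months. Section VI.C heads the analysis "Maintenance of gains (Y-BOCS, QIDS-SR, WSAS, Q-LES-Q-SF) at follow-up (week 24"), then specifies only between-arm contrasts at 12 months. It adds descriptive counts of responders retained, gained and lost by 12 months.

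**The concern.** Keeping a gain means not losing a meaningful part of it after week 12. A hypothesis of no significant difference says something else: that nothing detectable changed in either direction. The two part company in two situations.

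- **Patients keep improving.** A significant improvement after week 12 contradicts the hypothesis as worded, although it is the best result for durability. It is also plausible, because the app stays available during the 3-month follow-up.
- **Patients lose part of the gain and the estimate is imprecise.** A non-significant result agrees with the hypothesis without excluding the loss. Fewer week-24 completers make that agreement easier to reach.

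What is at stake is the durability statement for the app arm, which could be wrong in either direction. Adding the missing week-24 contrast to section VI would not help if it were then read by this criterion.

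**Working it through.** **The plan's own figure.** Section VI.D gives effect 0.76, SD 1.1, two-sided alpha 0.05, power 0.90 and 20% dropout. Two-sample t power from the noncentral t first reaches 0.90 at 46 per arm (power 0.906). Then 46 / (1 − 0.20) = 57.5, which rounds up to 58 per arm, or 116 in total. This matches the stated 116, so 0.76 and 1.1 are on one scale (0.76 / 1.1 = 0.69 SD). The plan gives no power or margin for Aim 3.

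**Inputs for the Aim 3 illustration**
- n = 60 × 0.80 = 48 app-arm completers, from 120 randomised 1:1 (section III) and 20% dropout by end of treatment (section VI.D).
- SD 1.1 at both visits (section VI.D).
- Correlation r between weeks 12 and 24: not in the document; assumed 0.5 to 0.7.
- Two-sided alpha 0.05, the natural reading of the hypothesis.
- Yardstick 0.76. This is a between-arm effect, used only because the document gives no expected gain within the app arm.

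**Formulas.** SD of change = 1.1 × √(2(1 − r)). SE = SD of change / √48. Smallest significant observed change = t(0.975; 47 df) × SE, with t = 2.012. The chance of significance for a true change d comes from the noncentral t with noncentrality d / SE.

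| | r = 0.5 | r = 0.6 | r = 0.7 |
|---|---|---|---|
| SD of change | 1.100 | 0.984 | 0.852 |
| SE | 0.159 | 0.142 | 0.123 |
| Smallest significant change | 0.319 | 0.286 | 0.247 |
| As a share of 0.76 | 42% | 38% | 33% |
| Improvement of 0.38: significant | 65% | 75% | 86% |
| Loss of 0.38 (half of 0.76): missed | 35% | 25% | 14% |
| Loss of 0.253 (a third of 0.76): missed | 65% | 58% | 48% |

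The test is symmetric, so the improvement row is one minus the half-loss row.

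**Effect of fewer completers.** At r = 0.5, a loss of 0.38 is missed 25% of the time with n = 60, 35% with n = 48 and 55% with n = 30. The n = 48 applies the end-of-treatment dropout rate; further attrition by week 24 would move results towards agreement with the hypothesis.

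**Does section VI supply a better rule?** No. Its contrast is between arms and at 12 months. Its responder counts do separate improvement from loss, but only descriptively and only at 12 months.

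**The case against.** The strongest reply is that no decision rule exists to criticise. Aim 3 states a prediction. For H3.1 (dropout) and H3.2 (satisfaction) the plan says outright that a non-significant result will be taken as success; for Aim 3 it does not. A reader might infer that the sponsor has committed to declaring gains maintained on a non-significant test, or to declaring failure on a significant improvement. The document does not support that inference, and this part of the reply stands. What remains is that the sentence is the only week-24 maintenance criterion given.

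Second, section VI plans no within-arm comparison of week 12 with week 24. This also stands: the error rates above describe the Aim 3 criterion, not a planned analysis. If the sections were reconciled wholly towards the 12-month between-arm contrast, the sentence would disappear. As written, both section II and the VI.C heading still say week 24.

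Third, two-sidedness is not stated for this exploratory aim. The two-tailed sentence covers the primary and secondary outcomes, and H3.1 and H3.2 use one-tailed tests. The improvement half of the point depends on a two-sided reading. That is what the undirected wording implies, but it remains a reading.

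Fourth, the aim is exploratory, and 0.76 is not the app arm's own gain. Both are correct. They limit the severity and make the figures illustrative, but leave the logical flaw in place.

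**Conclusion.** The point holds as a flaw in how Aim 3 is worded. The criterion has no direction and no margin, and nothing elsewhere in the document provides one for week 24. On the stated assumptions it would be contradicted by a further improvement of 0.38 in 65% to 86% of trials. It would be satisfied despite a loss of half of 0.76 in 14% to 35% of trials, and despite a loss of a third in 48% to 65%. These ranges rest on n = 48, SD 1.1, a two-sided 5% test and an assumed correlation of 0.5 to 0.7.

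A reader might go further and infer that most relapse would go unnoticed. The figures do not show that: at n = 48 and the same correlations, a loss of three quarters of 0.76 is missed at most 6% of the time. The exposure on the loss side is to partial losses. Nor does the point touch the primary or secondary conclusions at week 12. Severity is minor to moderate.

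**What to change.** 1. Replace the no-significant-difference hypothesis with a one-directional one: in the app-CBT arm, outcomes at week 24 have not worsened from week 12 by more than a pre-stated bound.
2. In the mixed model already planned with follow-up visits (section VI.C, Exploratory endpoint 2), add the app-arm contrast of week 24 with week 12. Report the change with its 95% confidence interval for each of the four outcomes.
3. Call gains maintained only if the interval excludes worsening beyond the bound. Count further improvement as maintained. If the interval includes both no loss and the bound, report the result as inconclusive.
4. State the bound in fixed scale points for each outcome, or as a share of the arm's gain. A share must be tested as one linear contrast, because the gain is itself estimated and shares the week-12 data. For a half-gain bound on a scale where lower is better, the contrast is week 24 − 0.5 × week 12 − 0.5 × baseline, and its upper limit must lie below zero. Reverse the sign for Q-LES-Q-SF. Half is only an example; the sponsor must justify the share.
5. Reconcile week 24 (section II and the VI.C heading) with the 12-month hypothesis and contrast in sections VI.B and VI.C.

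The cost is a reworded hypothesis and one extra contrast per outcome, with no new data. The bound must be fixed in advance, and the result may be inconclusive. With no true change, a fixed bound of 0.38 and n = 48, the chance of concluding maintenance is about 65% to 86% for r from 0.5 to 0.7. This is the same calculation as the improvement row above. A tighter bound would lower it.

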Mini International Neuropsychiatric Interview (M.I.N.I.): The M.I.N.I. (Sheehan et al., 2006) is a semi-structured diagnostic assessment of DSM-5 psychiatric illnesses. The M.I.N.I. is efficient, reliable, and well-validated.

Assessment of OCD and Related Symptoms

Yale-Brown Obsessive Compulsive Scale (Y-BOCS): The Yale-Brown Obsessive Compulsive Scale (Y-BOCS); Goodman, Price, Rasmussen, & Mazure, 1989) is a 10-item, clinician-administered measure of OCD symptom severity, which will be our primary outcome

measure. The Y-BOCS assesses individuals' obsessions and compulsions on a scale ranging from 0-4. At the screening visit, clinicians will administer a checklist to preliminary assess which obsessions and compulsions are present.

Obsessive Compulsive Symptoms Rating Scale (OCSRS): The OCSRS ([name] & Steketee, 2006) is a self-report measure of the severity of specific OCD symptom domains.

Clinical Global Impression – Improvement Scale (CGI-I) and severity scale (CGI-S) (Appendix): This rating scale, which ranges from 1 (very much improved) to 7 (very much worse), is commonly used in clinical trials (Guy, 1976). Participants will complete a CGI for OCD symptoms (CGI-P OCD) and the clinician will complete a CGI for OCD symptoms (CGI-OCD) and overall symptoms (CGI-global). The CGI will be a secondary outcome measure and will also be used to determine clinical deterioration of OCD (see Minimizing Risks, below). The CGI also has a severity scale (CGI-S) which is rated by the clinician at baseline. The CGI-S determines the patient's level of severity, in comparison to others the clinician has treated or assessed with the same diagnosis.

Patient Health Questionnaire-2 (PHQ-2) (Appendix): The PHQ-2 (Kroenke & Spitzer, 2002) self-report measure of depression severity includes 2 Likert scale items ranging from 0 (*not at all*) to 3 (*every day*). The 2 items are taken from the longer PHQ-9 measure and are selected because they assess the core diagnostic symptoms of depression. The PHQ-2 will be administered weekly via the app (or REDCap for those in the control condition) to monitor changes in depression symptom severity.³

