App Feedback Questionnaire (Midpoint) (Appendix): These multiple choice and open-ended questions ask participants to describe their ongoing perceptions of the app at midpoint (e.g., "How easy are the exercises to understand, overall?"")

App/Website Feedback Questionnaire (Endpoint) (Appendix): This self-report form collects participant feedback pertaining to the content and aesthetics of the app or website.

Endpoint Technologist Interview Notes (Appendix): This interview guide asks about credibility/expectancy, client satisfaction, and improvements at Week 12 Endpoint

Treatment Condition Questionnaire (Appendix): This brief measure will be used to assess whether the independent evaluator believes each subject was assigned to either CBT or HealthWatch as well as their confidence in this belief. This questionnaire will be completed at the end-of-treatment time point. This measure is based on Bang's 2x5 Blinding Index (Bang et al., 2004).

Life Events Questionnaire (Appendix): This question will be used to assess whether any major life events occurred that might have had a psychological impact on the subject.

COVID-19 Impact Questionnaire (Appendix): This 18 item self-report questionnaire asks participants about the impact of the coronavirus pandemic on their lives (e.g., "The COVID-19 pandemic and its impact have made my symptoms worse."). This measure will be administered to participants for all assessment visits.

Generalized Anxiety Disorder Screener (GAD-7, with COVID item) (Appendix): The original 7-item self-report questionnaire asks participants about anxiety symptoms experienced in the past two weeks. It has good to excellent internal consistency (Spitzer et al 2006; Loewe et al., 2008) and good convergent validity with other anxiety scales (Spitzer et al., 2006). We added one additional item to ask participants to self-rate how much their anxiety changed relative to before the COVID-19 pandemic. This measure will be administered to participants for all assessment visits.

Substance Use Questionnaire (with COVID item) (Appendix): This 2-item self-report questionnaire with 4 logic-branched follow-up questions asks participants about past month alcohol and other substance use. This measure will be administered to participants for all assessment visits.

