Mobile App Rating Scale: User Version (uMARS) (Appendix): This 23-item user-rated scale contains 4 objective quality subscales—engagement, functionality, aesthetics, and information quality—as well as a subjective quality rating. The MARS has shown high levels of interrater reliability for evaluating the quality of mHealth apps (Stoyanov et al, 2015). This measure will be completed at the end-of-treatment time point.

Wi-Fi Questionnaire: This 1-item measure sent weekly via Beiwe assesses whether the participants has connected to Wi-Fi so that study data can be downloaded. This feature is a tech requirement of the Android and iOS platforms.

Self-Help Questionnaire: This question will be used to assess what types of self-help programs an individual has engaged in (e.g. exercise, self-help books or non-OCD apps, peer-support groups)

IE Training and Qualifications, and Procedures to Ensure Assessment Integrity and Interrater Reliability: Assessments will be conducted by an independent evaluator (IE) who has a Masters or Doctoral degree in clinical psychology or related mental health field and will be employed at MGH. The IE will be otherwise uninvolved in study procedures. Training and reliability checks will be done to ensure that IEs conduct ratings in a uniform way. IEs will first receive instruction in the MINI, and Y-BOCS, from [name] or another gold-standard expert rater, prior to beginning as an IE. The IE will be supervised twice monthly by the PI. The IE will be required to demonstrate reliability on the Y-BOCS at a criterion of .80 ICC and 100% agreement on OCD diagnosis on the MINI, compared to measures rated by [name] or another gold-standard rater. All assessments will be audiotaped for reliability ratings. Names will not be included on digital recordings. To reduce rater drift, a trained reliability rater meeting the same qualifications as the IE will review 15% of randomly selected audiotaped interviews. If reliability falls below .75, we will institute retraining procedures.

Neurocognitive Computer Tasks

Participants will have the option to complete a set of computer tasks (the Stroop and Wisconsin Card Sorting Tasks), which will be administered via *Inquisit* by Millisecond, an online platform for precision psychological testing. To access the tasks, participants will be provided with a link and unique participant ID to log in. The tasks take about 15 minutes total and will be completed on a computer at home.

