Figure 1. Data flow and storage chart –Overview of All Data Sources.

See

Figures 2-14 in “Independent Monitoring of Source Data” for a detailed diagram and description of the data flow and storage described above in Figure 1. The administrative interface to this system will only be accessible to work stations on the PHS/MGH network. Of note, the CBT app architecture and code base were previously evaluated in #2017P000293, which is exactly equivalent to that described here. Similarly, the substantially equivalent REDCap and Beiwe flow and storage have been previously evaluated in #2017P000293 and #2019P002041 respectively.

Minimizing of Risks and Safety Reporting

The following procedures will be implemented to protect participants against risks. The information provided in this section pertains to all study phases, unless otherwise indicated.

1. Participants with active suicidal ideation at the screening assessment will be excluded from participating (see Inclusion/Exclusion Criteria). If a subject scores ≥ 21 on the

QIDS-SR and/or >1 on the self-report suicide questionnaire, the independent evaluator will follow up with a phone evaluation within 24 hours and refer the participant to a higher level of care if clinically indicated. Suicidal ideation at screening is also measured using the C-SSRS (see Inclusion/Exclusion criteria), and if a potential participant scores ≥ 2 , a study clinician, PI, or independent evaluator will conduct a risk evaluation with the participant and refer the participant to a higher level of care if clinically indicated.

2. Participants with severe major depressive disorder will be excluded from participating (see Inclusion/Exclusion criteria).
3. A disclaimer that is accessible from the home page of the digital CBT program and control condition website will be presented to remind participants that if they are experiencing suicidal thoughts, they should seek professional help or go to the emergency room right away. Links to 988, 911 and suicide hotline numbers will be provided along with this disclaimer.
4. A general resources page will be available on the app and website at all times to participants, which will include a suicide hotline number.

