5. Participants' clinical improvement or deterioration will be assessed weekly via a participant-rated CGI-OCD collected via the app in the app-based CBT group or REDCap surveys in the supportive attentional control condition. Participants may be withdrawn from the study if their clinical condition deteriorates substantially. Deterioration will be defined by a rating of 6 (much worse) or 7 (very much worse) on the patient -rated CGI during three consecutive, weekly assessments and (2) PI judgment that remaining in the study is not in the participant's best interest. Of note, three consecutive weekly ratings of 6 or 7 on the weekly, participant-rated CGI-OCD will also trigger a notification to the clinician via text message or email. In the case that a BA-level coach is notified that a participant's CGI indicates deterioration, they will notify a doctoral-level clinician as soon as possible (and within 24 hours). A study clinician will follow up with a phone evaluation within 24 hours of the alert and refer the participant to a higher level of care if clinically indicated.
6. Ratings on a one-item self-report suicide questionnaire will be carefully monitored weekly via the app in the app-based CBT group or REDCap surveys in the supportive attentional control condition; a score >0 at any assessment will trigger a pop up message to be presented to the patient within the mobile app reminding participants that if they are experiencing suicidal thoughts, they should seek professional help or go to the emergency room right away. Links to 988, 911, as well as a national suicide hotline, will be provided within this popup notification. A score >1 will also trigger notification to the clinician/coach via text message or email. In the case that a BA-level coach is notified that a participant reported a score >1 , they will notify a doctoral-level study clinician as soon as possible (and within 24 hours). A study clinician, PI, or independent evaluator will follow up with a phone evaluation within 24 hours of the alert and refer the participant to a higher level of care if clinically indicated. To be able to determine which participant triggered the alert (i.e., to link the de-identified trigger with the actual

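### The evaluator who rates the Y-BOCS is described as having no other study role, yet is listed as a possible caller after weekly in-trial alerts; nothing keeps such a call from revealing the arm

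*Combined protocol and SAP*

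**What the plan says.** Under Measures Descriptions, the Y-BOCS is a "clinician-administered measure of OCD symptom severity, which will be our primary outcome" measure. The IE paragraph in Study Procedures gives the assessments to the IE and adds: "The IE will be otherwise uninvolved in study procedures".

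Three other places deal with risk calls:

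- Section VII.D, Minimizing of Risks and Safety Reporting, item 6, on weekly suicide-item scores above 1: "A study clinician, PI, or independent evaluator will follow up with a phone evaluation within 24 hours of the alert".
- Item 1 of the same list, on a QIDS-SR of 21 or more and/or a suicide-item score above 1: "the independent evaluator will follow up with a phone evaluation within 24 hours". The list is introduced with: "The information provided in this section pertains to all study phases, unless otherwise indicated".
- The Suicide item entry under Measures Descriptions gives the call after a score above 1 to the clinician and does not mention the IE.

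The Treatment Condition Questionnaire, completed at end of treatment and based on Bang's blinding index, is there to "assess whether the independent evaluator believes each subject was assigned to either CBT or HealthWatch". This is the only place in the plan's text that refers to blinding.

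**The concern.** The primary test is the week-12 treatment contrast on a scale scored by an interviewer's judgement. Participants cannot be blinded to an app or a website, so protection against expectation in the ratings rests on the rater not knowing the arm. The IE paragraph offers that protection by keeping the rater out of everything else, and item 6 makes an exception to it without saying so.

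An IE who learned the arm through a risk call could then rate the same participant at week 6, week 12 or either follow-up. Knowledge of the arm could move the Y-BOCS and the clinician CGI-I toward the expected result. The participants concerned would be those who triggered an alert, not a random subset.

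**Working it through.** The plan states no figure on this point, so the main check is a comparison of the texts.

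1. **Can the call fall after randomization?** Yes under item 6. The Measures Chart lists the suicide item as weekly, with no baseline entry, and item 6 describes its collection separately for the two arms. Item 1 is less clear. Its sentence about the IE sits between two sentences about screening and uses the same QIDS-SR cut-off as the exclusion criterion. Against that, the list is said to cover all phases and the suicide item is not charted at baseline. The point does not need item 1.
2. **Can the call reveal the arm?** It can. The suicide item arrives through the app in one arm and REDCap in the other. Item 6 sends the alert to the clinician or coach, and coaches know the arm they support. The participant also knows the programme. A QIDS-SR trigger would not reveal the arm by its channel, because that scale is collected in REDCap in both arms.
3. **Is there a safeguard?** None was found. The text does not hide the alert source from an IE, ask participants not to disclose their programme, or move later ratings to another rater after a call.
4. **Would the problem be seen afterwards?** Only in part. The arm guess is taken once, at end of treatment, and Section VI plans no analysis of it.

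**Illustration of scale, on assumed inputs only.** The number of completers comes from the power section: effect 0.76, SD 1.1, two-sided alpha 0.05, power 0.90. The normal formula gives 2 × (1.960 + 1.282)² / (0.76/1.1)² = 44.02, so 45 per arm; the t-test version gives 46 (power 0.906). With 20% dropout, 46/0.80 = 57.5, so 58 per arm and 116 in total, as the plan states.

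Let f be the fraction of participants whose later rating is made by an IE who learned the arm on a call, and b the net between-arm rating shift among them, in SD units. The bias in the contrast is f × b. The table gives the two-sided type I error of a nominal 0.05 t-test with 46 completers per arm.

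| f | b = 0.25 | b = 0.5 | b = 1.0 |
|---|---|---|---|
| 5% | 0.050 | 0.052 | 0.057 |
| 10% | 0.052 | 0.057 | 0.076 |
| 20% | 0.057 | 0.076 | 0.158 |

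Neither f nor b comes from the documents. The table shows only that the effect is negligible when such calls are rare and becomes material when they are frequent and the rating shift is large.

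**The case against.** The case for leaving this as a wording matter is fair in several respects. In item 6 the IE is the last of three alternative callers, and the alert is not addressed to the IE. The described content of the alert is the item response, tied to a de-identified ID; nothing says that a caller sees its source. The exclusions for suicidal ideation and severe depression should limit alerts. The IE already interviews every participant at weeks 6 and 12, when a participant could disclose the arm anyway. Interviews are recorded and 15% are re-rated. The text uses both the singular and the plural for evaluators, so the caller need not be the later rater.

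These points support low exposure but do not remove the conflict. Re-rating a random 15% checks agreement between raters and is not aimed at participants who were called. That disclosure may also occur at assessment visits is a reason for a rule on unblinding, not against one.

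A reader might take item 1 as proof that the IE alone will make in-trial calls. The documents do not support that, since the item can be read as concerning screening, before there is an arm to reveal. A reader might also infer that those called are the more severe OCD cases. The trigger is the suicide item, not the Y-BOCS, so this does not follow either.

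**Conclusion.** The point stands as an unresolved conflict in the text with a plausible route to unblinded rating of the primary outcome. It should be corrected, but it does not show that the primary result will be biased.

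The conclusion rests on two inferences. One is that blinding is intended: the plan never says so outright, but an arm-guess form for the evaluator has little purpose otherwise. The other is that a call can reveal the arm, which the arm-specific collection channel and the participant's own knowledge make possible but not certain.

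The size cannot be quantified from the documents. One could assume that 5–20% of one arm is rated by an unblinded IE with a shift of 2–3 Y-BOCS points, and obtain 0.05 × 2 = 0.1 to 0.20 × 3 = 0.6 points. Both inputs would be invented, and the first is a joint event (called by an IE, arm learned, later rated by that same IE) for which the documents give no rate. That range should not be read as an estimate.

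**What to change.** Reconcile the IE paragraph, the Suicide item entry, and items 1 and 6 of Minimizing of Risks and Safety Reporting, including whether item 1 applies only at screening. The risk call, its timing and the choice of caller remain the sponsor's decision. Then add to the plan:

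- a statement in the IE paragraph that IEs are blind to arm;
- a rule that an IE who has had a post-randomization risk call with a participant, or has otherwise learned the arm, does not do that participant's later Y-BOCS or CGI ratings where another already certified rater is available;
- a log of every unblinding, with date and route;
- a sensitivity analysis that repeats the week-12 contrast without ratings made by an unblinded IE. It supports the primary analysis and does not replace it, because the ratings removed are not a random subset.

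The cost is protocol wording, a short log and one extra model run. The downside is an occasional change of rater within a participant, which adds some between-rater variance. If the reliability rater steps in, the independent drift check loses a little for those cases. The number of certified evaluators is not given, which is why the rule is conditional on availability.
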